16. PHARMACOKINETICS

The analysis of PK concentrations and parameters will be completed by a separate vendor.

17. SAFETY OUTCOMES

All outputs for safety outcomes will be based on the SAF. There will be no statistical comparisons between the treatment groups for safety data, unless otherwise specified in the relevant section.

17.1. ADVERSE EVENTS

Adverse Events will be coded using the latest version of MedDRA, down to the lower level term (LLT).

Treatment emergent adverse events (TEAEs) are defined as AEs that started or worsened in severity on or after the first dose of study medication. As AEs will be recorded up to 4 weeks after study drug treatment has ended, AE will be considered treatment-emergent even if started after the last dose date. Adverse

Document: \\iedc-vnasc01\BIOSdata\Abivax\ABX464\FZA92720\Biostatistics\Documentation\SAP\ABX464-103_SAP_V2.0_10MAY2021

Author: [REDACTED]

Version Number: 2.0
Version Date: 10May2021

Template No.: CS_TP_BS016 Revision 5

Reference: CS_WI_BS005

Effective Date: 01Apr2018

events occurring after Day 113 will be flagged in the AE listing.

An overall summary of number of patients within each of the categories described in the sub-sections below, as well as the number of occurrences of the AE will be provided as specified in the templates. Listings will include TEAEs and Non-TEAEs.

See APPENDIX 3 for handling of partial dates for AEs. In the case where it is not possible to define an AE as treatment emergent or not, the AE will be classified by the worst case; i.e. treatment emergent.

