Study Design and Methodology	
This phase IIb study will evaluate the efficacy and the safety of 3 dose-levels of ABX464, administered daily in improving Modified Mayo Score (MMS) in patients with moderate to severe Ulcerative Colitis at Week 8.
 
Eligible patients will be randomized into 4 parallel intervention/treatment groups:
 
  
 Intervention/treatment Active Arm	
   
 Group #1: 25mg qd	1 capsule of 25mg ABX464 + 1 capsule of Placebo	
 
 Group #2: 50mg qd	1 capsule of 50mg ABX464 + 1 capsule of Placebo	
 
 Group #3: 100mg qd	2 capsules of 50mg ABX464	
 
 Group #4: Placebo	2 capsules of Placebo	
  
 
The study design is presented below:
 
At Week 16, regardless of their clinical/symptomatic response and the actual treatment/dose received, patients willing to continue the study treatment and eligible for enrollment will roll over in an Open Label Extension study (ABX464-104). In this extension study, all patients will be dosed with ABX464 50mg q.d. ABX464-104 is a separate clinical protocol subject to health authorities and ethics committee approvals.
 
In the present induction study (ABX464-103), randomization will be stratified according to the following stratification factors:
 
 1) US versus non-US patients 2) Patients without previous exposure to biological drugs or JAK inhibitors versus 			Intervention/treatment Active Arm		Group #1: 25mg qd	1 capsule of 25mg ABX464 + 1 capsule of Placebo	Group #2: 50mg qd	1 capsule of 50mg ABX464 + 1 capsule of Placebo	Group #3: 100mg qd	2 capsules of 50mg ABX464	Group #4: Placebo	2 capsules of Placebo
Intervention/treatment Active Arm													
Group #1: 25mg qd	1 capsule of 25mg ABX464 + 1 capsule of Placebo												
Group #2: 50mg qd	1 capsule of 50mg ABX464 + 1 capsule of Placebo												
Group #3: 100mg qd	2 capsules of 50mg ABX464												
Group #4: Placebo	2 capsules of Placebo												

Study n°	ABX464-103	Clinical Phase	IIb	Type of Study	Safety, Efficacy, Dose-Ranging Study

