Premature trial discontinuation	
Patient's premature trial discontinuation could occur for the following reasons:
 
 ▪ Investigator's decision; patient that would experience a treatment failure during the study may be withdrawn at any time. S/he will have to be treated according to standard of care as soon as s/he is off from study treatment; ▪ An Adverse Event or an intercurrent condition that preclude continuation of treatment: 
 ○ Specifically, an increase \geq 3.0 x ULN in liver transaminases (AST/SGOT and/or ALT/SGPT) or an increase \geq 2.0 x ULN in Alkaline phosphatase or in total bilirubin requires close observation with repeating liver enzymes and serum bilirubin tests two times weekly and clinical investigation to understand the etiology of this elevation. Frequency of retesting can decrease to once a month if the abnormality stabilizes after this initial two weeks of follow-up and if the patient is asymptomatic. Discontinuation of the study treatment should occur if: 
 ▪ ALT or AST $>$ 8xULN ▪ ALT or AST $>$ 5xULN for more than 2 weeks ▪ ALT or AST $>$ 3xULN and total bilirubin $>$ 2xULN or INR $>$ 1.5 ▪ ALT or AST $>$ 3xULN with appearance of fatigue, nausea, vomiting, right upper quadrant pain or tenderness, fever, rash, and/or eosinophilia ($>$ 5%). 		

Study n°	ABX464-103	Clinical Phase	IIb		
	Type of Study	Safety, Efficacy, Dose-Ranging Study			
	
 ▪ Worsening of the UC defined, from Week 8 onwards, as a 2-point increase in the pMMS, with pMMS ≥ 4 on 2 separate occasions 7 day-apart and confirmed by an endoscopy sub-score of 2 points or higher; ▪ Major protocol violation; ▪ Patient's decision; ▪ Withdrawal of consent. 				
Patient Follow-up	
On Day 113 +/- 4 days, eligible patients willing to continue study treatment will be able to take part in an Open Label Extension study (ABX464-104). In this extension study, all patients will be dosed with ABX464 50mg QD. ABX464-104 maintenance study is a separate clinical study requiring health authorities and ethics committees' approvals.
				

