8.5. Time Period, and Frequency of Detecting AEs and SAEs

All AEs and SAEs occurring from the time a patient consents to participate in the study until 4 Weeks after he or she has completed or discontinued the investigational medicinal product must be recorded in the Patient's eCRF.

Moreover, any occurrence of pregnancy within 3 months post stopping dosing must be reported.

Importantly, SAEs will have to be reported, either by email or by Fax, to IntuVigilance Limited within 24 hours of awareness of an SAE.

IntuVigilance Limited

[name]
Hotline phone: [REDACTED]

Email Address: [REDACTED]

Fax number: [REDACTED]

Legislative guidance requires the investigator to also ensure that any **related** SAEs are reported after the patient finished the study if the investigator becomes aware of them.

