5.2.2. SAFETY ANALYSIS SET [SAF]

The Safety Analysis Set (SAF) will include all randomized patients who have received at least one dose of the study treatment. If there is any doubt whether a patient was treated or not, they will be assumed treated for the purposes of analysis. The SAF will be used for all safety analyses and patients will be analyzed as treated. Should a subject be exposed to two different treatment doses during the study, the subject will be analyzed according to the treatment received most of the time. This will be confirmed on

Document: \\ieddc-vnasc01\BIOSdata\Abivax\ABX464\FZA92720\Biostatistics\Documentation\SAP\ABX464-103_SAP_V2.0_10MAY2021

Author: [REDACTED]

Version Number:

2.0

Version Date:

10May2021

Template No.: CS_TP_BS016 Revision 5

Reference: CS_WI_BS005

Effective Date: 01Apr2018

a case-by-case basis at the BDR meeting.

The following patients will be excluded from this Analysis Set:

- Patients who have not received at least one dose of the study treatment:

CRITERION [3]: Randomized but no dose of ABX464 or Placebo Taken
DEVIATION STATUS: Major.
NOTES: 
• This criterion will be tested using the following data, as captured on the Exposure (EC) and drug accountability (DA) eCRF:
• The start date of study medication, as obtained from raw.EC.ECSTDAT.• Number of capsules dispensed and returned, as obtained from raw.DA.DAORRES4 and DAORRES5.

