APPENDIX 3. PARTIAL DATE CONVENTIONS

Imputed dates will NOT be presented in the listings.

ALGORITHM FOR TREATMENT EMERGENCE OF ADVERSE EVENTS:

START DATE	STOP DATE	ACTION
Known	Known/Partial/Missing	If start date < study med start date, then not TEAE If start date >= study med start date, then TEAE
Partial, but known components show that it cannot be on or after study med start date	Known/Partial/Missing	Not TEAE
Partial, could be on or after study med start date	Known	If stop date < study med start date, then not TEAE If stop date >= study med start date, then TEAE
	Partial	Impute stop date as latest possible date (i.e. last day of month if day unknown or 31st December if day and month are unknown), then: If stop date < study med start date, then not TEAE If stop date >= study med start date, then

Document: \\ieedc-vnasc01\BIOSdata\Abivax\ABX464\FZA92720\Biostatistics\Documentation\SAP\ABX464-103_SAP_V2.0_10MAY2021

Author: [REDACTED]

Version Number: 2.0
Version Date: 10May2021

Template No.: CS_TP_BS016 Revision 5

Reference: CS_WI_BS005

Effective Date: 01Apr2018

START DATE	STOP DATE	ACTION
		TEAE
	Missing	Assumed TEAE
Missing	Known	If stop date < study med start date, then not TEAE If stop date >= study med start date, then TEAE
	Partial	Impute stop date as latest possible date (i.e. last day of month if day unknown or 31st December if day and month are unknown), then: If stop date < study med start date, then not TEAE If stop date >= study med start date, then TEAE
	Missing	Assumed TEAE

ALGORITHM FOR PRIOR / CONCOMITANT MEDICATIONS:

START DATE	STOP DATE	ACTION
Known	Known	If stop date < study med start date, assign as prior If stop date >= study med start date and start date <= end of treatment, assign as concomitant

Document: \\ieedc-vnasc01\BIOSdata\Abivax\ABX464\FZA92720\Biostatistics\Documentation\SAP\ABX464-103_SAP_V2.0_10MAY2021

Author: [REDACTED]

Version Number: 2.0
Version Date: 10May2021

Template No.: CS_TP_BS016 Revision 5

Reference: CS_WI_BS005

Effective Date: 01Apr2018

START DATE	STOP DATE	ACTION
	Partial	Impute stop date as latest possible date (i.e. last day of month if day unknown or 31st December if day and month are unknown), then: If stop date < study med start date, assign as prior If stop date >= study med start date and start date <= end of treatment, assign as concomitant
	Missing	If stop date is missing could never be assumed a prior medication If start date <= end of treatment, assign as concomitant

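### SAP 17.1 and Appendix 3 do not end the treatment-emergent period at the first ABX464-104 dose, so an open-label event entered in the 103 database counts under the as-treated 103 arm, including placebo

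*SAP*

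**What the plan says.** SAP 17.1 treats an AE as treatment-emergent (a TEAE) if it began or worsened from the first dose on, and carries this past the end of dosing: "AE will be considered treatment-emergent even if started after the last dose date". The reason given is "As AEs will be recorded up to 4 weeks after study drug treatment has ended". The matching date rule in Appendix 3 is "If start date >= study med start date, then TEAE". For late events, the text of 17.1 offers only that "events occurring after Day 113 will be flagged in the AE listing".

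Safety patients are analysed as treated (SAP 5.2.2). For someone exposed to two doses, "the subject will be analyzed according to the treatment received most of the time".

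Protocol 8.5 says that AEs from consent "until 4 Weeks after he or she has completed or discontinued the investigational medicinal product must be recorded" in the eCRF. On rollover, the Protocol synopsis (Patient Follow-up) says: "On Day 113 +/- 4 days, eligible patients willing to continue study treatment will be able to take part" in ABX464-104. Its design section adds: "In this extension study, all patients will be dosed with ABX464 50mg q.d". Protocol 9.3 defines two TEAE periods, one up to Day 113 and one after it.

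**The concern.** For a patient who rolls over, the four weeks after the last 103 dose are not drug-free follow-up. They are the first weeks of open-label ABX464 50 mg. For a former placebo patient they are the first exposure to ABX464 at all, and Protocol 1.2.5.2 describes the commonest events (nausea, vomiting, headache) as arising after treatment starts.

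An event of that kind counted under placebo narrows the safety contrast between drug and placebo. In the same way, the 25 mg and 100 mg arms can collect events that occurred on 50 mg. Safety by dose against placebo is a stated secondary objective (Protocol 2.2).

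**Working it through.** The documents give no figure to reproduce, so the check is mainly of rules against each other.

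**1. Bounds of the period.** The lower bound is the first dose. The only upper bound is indirect: the four-week recording period mentioned in 17.1. Appendix 3 has no upper test for AEs, although its medication algorithm does compare start dates with the end of treatment. Neither AE text mentions ABX464-104.

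**2. When open-label dosing starts.** The first 104 dose date is not stated. Enrolment takes place at the Day 113 visit (Protocol 5.2.4), and rollover patients skip the Day 115 PK sample (5.3.11) and the End of Study visit (7.3). I infer that 104 dosing follows directly.

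**3. Existing safeguards.**
- The two-dose rule in SAP 5.2.2 moves whole subjects, not events. After 16 weeks of placebo, a patient stays under placebo.
- The two-period split of Protocol 9.3 appears in the SAP text only as the listing flag, and SAP 3.3 records no change. The table templates are not in the file.
- SAP 9 lists enrolment in ABX464-104. This allows a check by hand but does not alter a table.

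**4. Does a fixed Day 113 flag isolate open-label time?** Let v be the day of the Week 16 visit, 109 to 117. The documents disagree on the last dosing day: SAP 14 says Day 112, while Protocol 6.1 and 7.1 point to Day 113. Reading A puts the last 103 dose on v − 1 and the first 104 dose on v. Reading B puts them on v and v + 1. The flag covers Day 114 onward.

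| v | Reading A | Reading B |
|---|---|---|
| 109 | Days 109–113: 5 open-label days unflagged | Days 110–113: 4 unflagged |
| 113 | Day 113: 1 unflagged | 0 |
| 117 | Days 114–116: 3 days on 103 drug flagged | Days 114–117: 4 flagged |

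The flag also marks post-treatment events of patients who never roll over.

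**5. Share of the period.** For a completer who rolls over, share = 28 / (last 103 dose day + 28). This runs from 28/136 = 20.6% (Reading A, v = 109) to 28/145 = 19.3% (Reading B, v = 117). It is calendar time, not event frequency.

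**6. Patients at risk.** Protocol 1.3 reports that 22 of 32 Phase IIa patients (68.75%), and 7 of 9 on placebo (77.8%), entered the maintenance study. With 61 placebo patients, 0.6875 × 61 = 41.9 and 0.778 × 61 = 47.4, so about 42 to 47 would have a period that runs into open-label drug. One misattributed patient adds 1/61 = 1.64 points to that event's placebo rate.

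**7. Illustration under assumptions.** Let p0 be the 16-week placebo risk, r the rollover share, h the event risk in the first four open-label weeks, and c the share of such events entered in the 103 database. The tabulated placebo incidence is then p0 + (1 − p0) × r × h × c. The values of p0, h and c are assumptions, not document figures. With p0 = 5% and c = 1:

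| h | r = 22/32 | r = 7/9 |
|---|---|---|
| 5% | 8.3% | 8.7% |
| 10% | 11.5% | 12.4% |
| 20% | 18.1% | 19.8% |

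With c = 0 the incidence stays at 5%. The documents do not locate c between 0 and 1.

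**The case against.** The strongest reply is that the harm depends on a fact outside the file. ABX464-104 is a separate protocol whose AE rules and data flow are not shown. If it captures everything after rollover, nothing is misattributed in 103. Protocol 8.6 collects AEs at study visits, and rollover patients have no 103 visit after Week 16. Protocol 8.5 runs from completion or discontinuation of the product, while rollover patients are described elsewhere as continuing study treatment, so its application to them is open to argument. This stands as a limit on size. It does not remove the fault: read as written, 8.5 sets a recording duty without a rollover exception, and the SAP then counts whatever was recorded.

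A second reply is that the Protocol 9.3 split may be in the templates. That cannot be excluded. A split at a fixed Day 113 would still miss open-label days of patients who switch earlier, and would still mix the two kinds of late event.

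A third is that cutting at the first 104 dose loses information. Protocol 1.2.4 gives the metabolite a half-life of 90 to 110 hours. Five half-lives are 5 × 90 / 24 = 18.8 to 5 × 110 / 24 = 22.9 days, so late events from 103 drug are plausible. This stands and belongs in the fix as a stated cost.

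A reader might go further and infer that the placebo safety results will be contaminated, or that the SAP has discarded the protocol's two periods. The documents support neither: capture is unknown and the templates are unseen. Nor is the period unlimited, since the four-week recording rule bounds it.

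**Conclusion.** The concern holds as a fault in the rule. Followed literally, SAP 17.1 and Appendix 3 make any AE that starts in the four weeks after the last 103 dose, and is entered in the 103 database, a TEAE of the as-treated 103 arm, even when it occurred on open-label ABX464 50 mg. The arm is the as-treated one under SAP 5.2.2, not the randomised one; for correctly dosed patients the two coincide.

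The size is unknown and may be zero. The conclusion assumes that 104 dosing starts at or just after the Week 16 visit and that at least some post-rollover events reach the 103 database. The Phase IIa rollover shares come from a small study and count patients at risk, not misattributed events.

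A reader might infer that the efficacy conclusion is touched. It is not: the primary endpoint is at Week 8, before rollover. SAP 17 treats the safety comparison as descriptive unless otherwise specified. The change should still be made before unblinding, because placebo is the reference for every safety contrast.

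**What to change.** - End the 103 TEAE period at the earlier of four weeks after the last 103 dose or the first 104 dose. Add this upper bound to the AE algorithm in Appendix 3.
- Tabulate on-treatment and post-treatment TEAEs separately, using each patient's actual last 103 dose date instead of calendar Day 113, so that arms can be compared on the on-treatment period. Set the listing flag by the same dates.
- List post-rollover events separately, and state which study's database holds them.
- Record the change in SAP 3.3.
- Reconcile the Day 112 statement (SAP 14) with the Day 113 statements (Protocol 6.1, 7.1) on the last dosing day.

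The cost is one date imported from the 104 study, one line in Appendix 3, one table split and one entry in SAP 3.3. The downside is that rollover patients have a shorter post-dose window than the others, so late events from 103 drug in those patients appear only in the separate listing. The share who roll over may also differ by arm, which is why the on-treatment table should carry the comparison.

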17.1.1. ALL TEAES

Incidence of TEAEs will be presented by SOC and PT and also broken down further by maximum severity and relationship to study medication.

17.1.1.1. Severity

Severity is classed as mild, moderate, severe, life-threatening and fatal corresponding to the Common Terminology Criteria of Adverse Events (CTCAE) grades 1 to 5 (increasing severity) (Version 5.0 or most recent version). TEAEs starting after the first dose of study medication with a missing severity will be classified as severe. If a patient reports a TEAE more than once within that SOC/PT, the AE with the worst-case severity will be used in the corresponding severity summaries.

17.1.1.2. Relationship to Study Medication

Relationship, as indicated by the Investigator, is classed as Unrelated, Unlikely to be Related, Possibly Related, Probably Related and Related (increasing severity of relationship). TEAES will be summarized as “Related” or “Unrelated”. A “related” TEAE is defined as a TEAE with a relationship to study medication as “possibly related”, “probably related” or “related” to study medication, and an “unrelated” TEAE is either “unrelated” or “unlikely to be related” to study medication. TEAEs with a missing relationship to study medication will be regarded as “probably related” to study medication. If a

Document: \\iedc-vnasc01\BIOSdata\Abivax\ABX464\FZA92720\Biostatistics\Documentation\SAP\ABX464-103_SAP_V2.0_10MAY2021

Author: [REDACTED] Version Number: 2.0
Version Date: 10May2021

Template No.: CS_TP_BS016 Revision 5

Reference: CS_WI_BS005

Effective Date: 01Apr2018

patient reports the same AE more than once within that SOC/ PT, the AE with the worst-case relationship to study medication will be used in the corresponding relationship summaries.

17.1.2. SERIOUS ADVERSE EVENTS

Serious adverse events (SAEs) are those events recorded as “Serious” on the Adverse Events page of the eCRF. A summary of serious TEAEs by SOC and PT will be prepared, as well as related treatment-emergent SAEs by maximum severity will be prepared. A listing of all SAEs will also be presented.

17.1.3. TEAES LEADING TO DISCONTINUATION OF STUDY MEDICATION

TEAEs leading to permanent discontinuation of study medication will be identified by using the response “Permanent discontinuation” to the question “Action taken with study treatment” on the AE page of the eCRF. For TEAEs leading to discontinuation of study medication, summaries of incidence rates (frequencies and percentages) by SOC and PT will be prepared.

17.1.4. TEAES LEADING TO DISCONTINUATION FROM STUDY

TEAEs causing the patient to discontinue from the study will be identified by a positive response to the question “Did the AE cause the patient to discontinue from the study?” and will be summarized by SOC and PT.

17.1.5. ADVERSE EVENTS LEADING TO DEATH

TEAEs leading to death are those events which are recorded as 'Fatal' on the Adverse Events page of the eCRF. A summary of TEAEs leading to death by SOC and PT will be prepared.

17.1.6. ADVERSE EVENTS OF SPECIAL INTEREST

Treatment-emergent adverse events of special interest (AESI) associated with treatment with ABX464

Document: \\ieedc-vnasc01\BIOSdata\Abivax\ABX464\FZA92720\Biostatistics\Documentation\SAP\ABX464-103_SAP_V2.0_10MAY2021

Author: [REDACTED]

Version Number: 2.0
Version Date: 10May2021

Template No.: CS_TP_BS016 Revision 5

Reference: CS_WI_BS005

Effective Date: 01Apr2018

include skin lesions and headache episodes lasting longer than a week and refractory to standard painkillers and will be recorded as an AE of interest on the eCRF AE form. A summary of AESIs by SOC and PT will be prepared, as well as a further summary and listing of information on headache episodes, obtained from the Follow up Headache Questionnaire on the eCRF.

17.2. LABORATORY EVALUATIONS

Results from the central laboratory for hematology and biochemistry, including blood pregnancy tests will be included in the reporting of this study. A list of laboratory assessments to be included in the outputs is presented in Table F below.

The results of Fecal Calprotectin levels will not be communicated to the study Sponsor, Investigational Site or blinded biostatistical team during the study to avoid any possible bias related to disease evaluation. These results will be made available post DBL in the unblinded final analyses.

Presentations will use *Système International* (SI) Units.

Quantitative laboratory measurements reported as “< X”, i.e. below the lower limit of quantification (BLQ), or “> X”, i.e. above the upper limit of quantification (ULQ), will be converted to X for quantitative summaries, but will be presented as recorded, i.e. as “< X” or “> X” in the listings.

The following summaries will be provided for laboratory data:

- Actual and change from baseline by visit (for quantitative measurements)
- Shift from baseline according to laboratory approved normal ranges (Low, Normal, High) for quantitative measurements
- Incidence of clinically significant abnormalities
- Listing of patients meeting abnormal criteria

The following clinical laboratory parameters will be summarized using descriptive statistics (n, mean, SD,

Document: \\ieedc-vnasc01\BIOSdata\Abivax\ABX464\FZA92720\Biostatistics\Documentation\SAP\ABX464-103_SAP_V2.0_10MAY2021

Author: [REDACTED]

Version Number: 2.0
Version Date: 10May2021

Template No.: CS_TP_BS016 Revision 5

Reference: CS_WI_BS005

Effective Date: 01Apr2018

standard error of the mean [SEM], median, minimum and maximum.):

Table F Laboratory Tests

HEMATOLOGY	BIOCHEMISTRY	STOOLS
Basophils	Alanine Aminotransferase (SGPT)	Fecal Calprotectin
Basophils/100 Leukocytes	Albumin	
Eosinophils	Alkaline Phosphatase	
Eosinophils/100 Leukocytes	Aspartate Aminotransferase (SGOT)	
Erythrocyte Mean Corpuscular Hemoglobin Concentration	Bilirubin, Total	
Erythrocyte Mean Corpuscular Volume	Blood Urea Nitrogen	
Hematocrit	C Reactive Protein	
Hemoglobin	Calcium	
Lymphocytes	Chloride	
Lymphocytes/100 Leukocytes	Cholesterol, Total	
Monocytes	Creatinine	
Monocytes/100 Leukocytes	Creatinine Clearance (Est)	
Neutrophils	Gamma Glutamyl Transferase	
Neutrophils/100 Leukocytes	Glucose	
Platelets	Glutamate Dehydrogenase	
Red Blood Cells	HDL Cholesterol	
White Blood Cells	LDL Cholesterol	
	Lactate Dehydrogenase	
	Lipase	
	Phosphorus	
	Potassium	
	Protein	
	Sodium	

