5.3.8. Hematology and biochemistry

For hematology and biochemistry central laboratory will be used (i.e. Eurofins). All lab dosages will be done centrally. Sampling kits and transportation information and devices will be provided by Eurofins. Due to the outbreak of the SARS Cov-2 pandemic, some patients may not attend the study site, therefore hematology and biochemistry measurements may be done locally to assess the safety.

Regarding the calprotectin measurement, the local lab might be asked to keep back-up samples at -80°C till the end of the study.

The results of fecal calprotectin levels will not be communicated to either the study Sponsor or the Investigational site during the study in order to avoid any possible bias related to disease evaluation.

Each laboratory value that is outside of the central laboratory normal range will be identified. The Investigator will be responsible for assessing the clinical significance of laboratory abnormalities. If the Investigator is uncertain about the clinical significance of a laboratory abnormality, he/she will consult with the Sponsor medical monitor.

The Investigator should follow any clinically significant laboratory abnormalities until resolution.

Table displays the clinical laboratory parameters that must be measured.

Table 2: Laboratory Tests

HEMATOLOGY	BIOCHEMISTRY	STOOLS
Hemoglobin	Sodium	Fecal calprotectin
Hematocrit	Potassium	
WBC	Chloride	
Neutrophils	Calcium	
Lymphocytes	Phosphate	
Monocytes	Glucose	
Eosinophils	BUN or urea	
Basophils	Creatinine	
Platelet count	AST	
Prothrombin time (From D1 to D113 only)	ALT	
Fibrinogen (From D1 to D113 only)	GLDH	
	Lipase	
	Alkaline phosphatase	
	gGT	
	Total bilirubin	
	Total protein	
	Albumin	
	LDH	
	CRP	
	Total cholesterol	
	HDL cholesterol	
	LDL cholesterol	
	Troponin I & T (From D1 to D113 only)	

At each biochemistry time point, a tube containing the remaining serum (at least 1 mL) should be kept and stored at -20°C for potential further liver function parameters such as soluble caspase-cleaved keratin 18 (M30 Elisa) and/or miRNA22 as a marker of early hepatotoxicity.

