The imputed components will be used to derive the pMMS (Stool Frequency Sub score + Rectal Bleeding Sub score) and MMS (Stool Frequency Sub score + Rectal Bleeding Sub score + Endoscopy Sub score) at Week 8.

Missing safety data will not be imputed. Percentages based on the number of subjects with data available will not take missing observations into account.

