17.2.1. LABORATORY REFERENCE RANGES AND AGE CRITERIA

Quantitative laboratory measurements will be compared with the relevant laboratory reference ranges in SI units and categorized as:

- Low: Below the lower limit of the laboratory reference range.
- Normal: Within the laboratory reference range (upper and lower limit included).
- High: Above the upper limit of the laboratory reference range.

In addition to the high and low quantitative laboratory assignments (as identified by means of the laboratory reference ranges), abnormalities will be classified as not clinically significant or clinically

Document: \\ieedc-vnasc01\BIOSdata\Abivax\ABX464\FZA92720\Biostatistics\Documentation\SAP\ABX464-103_SAP_V2.0_10MAY2021

Author: [REDACTED]

Version Number:

2.0

Version Date:

10May2021

Template No.: CS_TP_BS016 Revision 5

Reference: CS_WI_BS005

Effective Date: 01Apr2018

significant.

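### The protocol allows local safety bloods during the pandemic, but the SAP names only central results and gives no rule for local values, so its laboratory tables could undercount abnormalities

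*SAP*

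**What the plan says.** Protocol 5.3.8 starts from a central default: "For hematology and biochemistry central laboratory will be used". The same section then adds a pandemic exception: "some patients may not attend the study site, therefore hematology and biochemistry measurements may be done locally to assess the safety". It gives no rule for classifying a local value; the only normal range it mentions is the central laboratory's.

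SAP 17.2 opens with the source of the laboratory data: "Results from the central laboratory for hematology and biochemistry, including blood pregnancy tests will be included in the reporting of this study". The outputs built on that source are values and changes by visit, a shift table ("Shift from baseline according to laboratory approved normal ranges (Low, Normal, High) for quantitative measurements"), "Incidence of clinically significant abnormalities", and a listing of patients who meet abnormal criteria. SAP 17.2.1 adds: "Quantitative laboratory measurements will be compared with the relevant laboratory reference ranges in SI units and categorized as" low, normal or high.

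SAP 7.3 says: "Missing safety data will not be imputed". SAP 3.3 lists departures from the protocol, including two on safety (ECG descriptive statistics and potentially clinically significant abnormalities), but says nothing about local laboratory results.

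**The concern.** The protocol allows local testing for one stated purpose, safety. The SAP section that reports laboratory safety names a source that does not cover those samples. A programmer who follows SAP 17.2 literally would take the central-laboratory data and stop there.

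Two protocol commitments are affected. Protocol 2.4 lists the number of clinically significant laboratory abnormalities per group as a secondary endpoint. Protocol 9.3 promises, for each parameter, the number of patients with at least one abnormal value, and does not restrict it to central results. If local values are left out, both could be too low, and the gap would fall on patients who could not attend the site.

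Liver chemistry makes this worth settling. Protocol 1.2.5.1 names the liver as a main target organ in the animal studies and says that a liver monitoring plan is in place. Transaminases and bilirubin are among the biochemistry tests that may be done locally.

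**Working it through.** The plan states no figure on this point, so the check is a comparison of text.

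**Step 1. Source allowed against source reported.**

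| Question | Protocol | SAP |
|---|---|---|
| Which laboratory? | Central, with local allowed because of the pandemic (5.3.8) | Central; no other named (17.2) |
| Which range for a local value? | Not stated; only the central range is mentioned (5.3.8) | The relevant range, in SI units; local ranges not mentioned (17.2.1) |
| Count of patients with at least one abnormal value | Promised, with no limit by source (9.3) | Shift table, built on the 17.2 data |
| Is leaving out local values a declared change? | Not applicable | No (3.3) |

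**Step 2. Does other SAP text bring local values in?** SAP 17.2.1 is neutral on source. SAP 6.3 lets unscheduled measurements count towards best or worst values, as in shift tables, but it deals with timing and not with which laboratory ran the sample. No SAP section mentions local results.

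**Step 3. What happens to a visit with only a local sample?** With no rule to use it, that visit has no value in the laboratory dataset. Under SAP 7.3 it is not imputed, and it drops out of any percentage based on available data. SAP section 7 allows either the analysis set and arm or the subjects with data as denominator. A count can therefore only fall. A percentage falls if the denominator is the arm, and can move either way if it is subjects with data.

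**Step 4. Is there another route?** Under protocol 8.4.1, a laboratory finding that the investigator judges clinically significant is recorded as an AE or SAE if it meets the definition, with no limit to central results. It would then appear in the AE tables of SAP 17.1. A local value that is out of range but not judged clinically significant has no such route.

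**Step 5. Size.** Let q be the share of visits with only a local sample. The documents do not give q. If abnormalities are equally frequent at local and central visits, a share q of abnormal visit values is missed. That does not carry over to patients. A patient abnormal at k visits is missed from the count only if all k were local:

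- local sampling independent between visits: q^k;
- each patient either always local or always central: q.

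With an assumed q = 10% and k = 2, the range is 0.10 × 0.10 = 1% up to 10%. With k = 1 it is 10% in both cases. The flow chart schedules these bloods on Days 8, 29, 57, 85 and 113, plus end of study where it applies and a follow-up sample, so a lasting abnormality has several chances to appear in a central sample. The true q could be close to zero.

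**The case against.** **The SAP does not say that local results are excluded.** A reader might infer a deliberate rule of central results only. The text does not support that: SAP 17.2 says that central results will be reported and is silent on any others. What stands is that it names one source and gives no means of using another.

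**Safety findings are not simply lost.** A reader might infer that liver or hematology signals seen locally would vanish from the report. Protocol 8.4.1 rules this out for findings judged clinically significant, which should reach the AE tables. The liver rules in protocol 7.2 also name no laboratory source. This objection largely stands: the loss is confined to the laboratory outputs and, beyond them, to abnormal values not judged clinically significant.

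**A local share of, say, 10% does not mean that 10% of abnormal patients are missed.** That would be a visit-level figure, on an assumed share. Protocol 9.3 counts patients, for whom the loss can be much smaller.

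**Central reporting follows the protocol's own default.** This is true, but the exception stands in the same section and was made for safety, so the SAP needs a rule for it.

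**The answer may lie in papers not available here.** SAP section 8 refers to output templates, and SAP section 18 to an eCRF version of 19 February 2021. Either might show that local values are captured. That cannot be checked, and the SAP text would still need to say so.

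**Pooling laboratories can create false shifts.** This stands for shift tables, where laboratory and range would change between baseline and follow-up. It applies much less to investigator-judged significance or to a value set against its own laboratory's range.

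**Conclusion.** The gap is real and minor. The protocol allows local safety bloods; the SAP names only central results for laboratory reporting, gives no rule for local values and does not declare their omission. Followed as written, it would leave local values out of the laboratory outputs and could undercount the clinically significant abnormality endpoint and the number of patients with at least one abnormal value.

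The size cannot be estimated, because no document says how many samples were local. The conclusion assumes that some local samples were taken and that the programming follows SAP 17.2 literally. The documents do not support a claim of intended exclusion, of safety signals missing from the report as a whole, or of any particular percentage lost.

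**What to change.** Amend SAP 17.2 as follows:

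- Count local results, flagged, in the incidence of clinically significant abnormalities, in the count of patients with at least one abnormal value, and in the abnormal-value listing. Classify each against the range of the laboratory that measured it.
- Keep means and changes from baseline central-only.
- Show the shift tables central-only, and add a version with local values as a sensitivity display. Give the count of patients with at least one abnormal value its own line, since protocol 9.3 places it inside the shift tables.
- Report the number of local samples per arm, so that a reader can judge how much depends on them.

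If local values are not in the database, say so in SAP 3.3 as a change from the protocol.

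The cost is collecting local reference ranges (from however many of the planned 110 to 150 sites used local testing), unit conversion, and some noise from mixing laboratories. No new patient procedure is needed. Protocol section 9 allows documented and signed SAP amendments before the final database lock.
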